**A study of lung ultrasound combined with
oxygenation index for precise extubation after
general anaesthesia in the elderly - a multicentre,
randomised, double-blind clinical trial**

Programme number: V4.0

Team leader: Tianjin First Central Hospital

Principal Investigator: [name]

Version date: 2022.11.4

Principal Investigator Programme Signature (Team Leader Unit)

Protocol name: Study of pulmonary ultrasound combined with oxygenation index for precise extubation after general anaesthesia in the elderly – a multicentre, randomised, double-blind parallel controlled clinical trial

Programme code: 20221104

Version number and date: 4.0, 4 November 2022

By signing this programme signature page, the investigator acknowledges and agrees that.

I have read the above research proposal and its annexes.

I agree to carry out the study in accordance with this study protocol and the ICH-GCP, local regulations and other applicable regulations to perform the relevant duties.

This document contains confidential information and will not be disclosed without written authorisation from the reporting party, except to those directly involved in the execution of the study or ethical/regulatory review.

I agree that I will ensure that all staff involved in this study are aware of their obligations in relation to the above commitments.

Research Unit: Tianjin First Central Hospital

[name]

Principal Investigator (in print) Principal Investigator (signature) Date of signature (year/month/day)

Programme Summary

Study Title	A study of lung ultrasound combined with oxygenation index for precise extubation after general anesthesia in the elderly - a multicenter, randomized, double-blind clinical trial.
Programme number	20221104
Version number and date	V4.0, 2022.11.04
Principal Investigator	Tianjin First Central Hospital, [name]
Senate Research Centre	5 tertiary hospitals
Purpose of the study	
Main research objectives
 
1. to evaluate the predictive value of LUS, MAPSE, TAPSE, DD and OI indicators for accurate postoperative extubation in elderly people undergoing general anaesthesia.
 
2. Explicit cardiac and pulmonary ultrasound combined with diaphragmatic mobility and oxygenation index is a good guide to cardiac and pulmonary complications after surgery in the elderly.

Study endpoints	The incidence of pulmonary complications at 7d postoperatively and mortality in patients at 30d postoperatively.

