Study population	Elderly patients admitted to the PACU with a tube after major surgery under general anaesthesia, aged ≥ 65 years, expected to be mechanically ventilated for ≥ 3 h and who have passed the clinician's withdrawal screening test.
Study design	
We joined hands with the Fourth Central Hospital of Tianjin, the Fifth Central Hospital of Tianjin, the TEDA Hospital of Tianjin, the First Hospital of Shanxi Medical University and the Cancer Hospital of Shanxi Province to conduct a multicentre prospective clinical trial of 200 elderly patients, aged ≥ 65 years, after general anaesthetic surgery.
 
Ultrasound examinations of the heart and lungs were performed on elderly post-operative patients who had passed the SBT trial and needed to be extubated. LUS, MAPSE, TAPSE and DD were calculated, and arterial blood was drawn to determine OI using a blood gas analyser. The ROC curves of the combined predictors of LUS, MAPSE, TAPSE, DD and OI were plotted, the area under the curve (AUC) was calculated, the optimal threshold value was selected, the sensitivity and specificity were calculated, and the predictive value of the above indicators was evaluated.

General information and clinical indicators: for elderly patients admitted to the resuscitation room after general anaesthesia, record the patient's name, gender, age, pH at the end of the SBT test, $\text{PaO}_2/\text{FiO}_2$, PaO_2 , PaCO_2 , tidal volume.

222 The patient's heart rate, respiration, blood pressure, tidal volume and other parameters are recorded, as well as the patient's subjective response (presence or absence of dyspnoea). After extraction, another arterial blood gas is drawn and the arterial partial pressure of oxygen is analysed, as well as the inhalation oxygen concentration, respiratory rate and exhalation tidal volume. Calculate the oxygenation index (P/F value) = arterial partial pressure of oxygen (PaO_2)/inhaled oxygen concentration (FiO_2).

Withdrawal Screening Test (SBT).

(1) The cause of the mechanical ventilation has improved or been removed.

(2) Oxygenation indicators: oxygenation index $\geq 150 \sim 300$; PEEP $\leq 5 \sim 8 \text{ cmH}_2\text{O}$; $\text{FiO}_2 \leq 0.4$; $\text{pH} \geq 7.25$; for patients with COPD: $\text{pH} > 7.30$, $\text{FiO}_2 < 0.35$, $\text{PaO}_2 > 50 \text{ mmHg}$.

(3) Haemodynamic stability, absence of dynamic changes in myocardial ischaemia and absence of significant hypotension.

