ventricular free wall to obtain a clear image of the mitral annular motion displacement, freeze and magnify this image, and measure the maximum mitral annular displacement (MAPSE) from end-diastole to end-systole. In the same way, the M-mode ultrasound sampling line was placed parallel to the ventricular septum as far as possible, at which point the sampling point was located at the tangent of the junction between the anterior tricuspid annulus and the free wall of the right ventricle, and the maximum end-diastolic to end-systolic displacement (TAPSE) of the tricuspid annulus was measured. After three consecutive measurements, the mean of these two parameters is calculated and the difference between them is then calculated to give the difference in annular plane systolic excursion difference (APSED) between the mitral and tricuspid annuli. (The normal value for TAPSE is 22-24 mm; for MAPSE the normal value is ≥ 13 mm in men and ≥ 11 mm in women.)

Diaphragm mobility check:

The patient was placed in a supine position, with the chest and upper abdomen exposed. After stable breathing, an ultrasound convex array probe was used to detect under the rib arch in the right midclavicular line, and the distance between the diaphragm and the body probe was recorded in M ultrasound mode, and the difference between the diaphragm movement in the inspiratory and expiratory phases was measured at the end of the SBT test and recorded as DD.

The group was divided into a successful extraction group and a failed extraction group according to the outcome of the withdrawal.

The criteria for successful extubation are as follows: observe the withdrawal of extubation for 48 h. Signs of respiratory distress, i.e. increased respiratory rate (RR), increased heart rate (HR) and decreased oxygen saturation (SpO_2) within 48 h. The need for non-invasive mechanical ventilation or high-flow nasal cannula oxygen therapy or even reintubation is considered a failure of extubation, otherwise the extubation is considered successful.

The incidence of cardiac and pulmonary complications at 7d postoperatively and the mortality rate of patients at 30d postoperatively were recorded.

	
(1) Age ≥ 65 years, regardless of gender. (2) Post-tracheal intubation, ventilator-assisted ventilation. (3) Performing general anaesthetic surgery. (4) Duration of mechanical ventilation ≥ 3h. (5) Successfully passed the Spontaneous Breathing Test (SBT).

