Exclusion criteria	
(1) Narrowing of the airway and compression of the airway. (2) Large breaks and burns to the skin of the chest. (3) Central respiratory failure. (4) Severe muscle weakness and absence of voluntary diaphragmatic activity. (5) Patients with unscheduled extubation. (6) Patients with combined end-stage cardiopulmonary disease.

Exit criteria	
Termination of the trial is required if the subject meets one or more of the following criteria.
 
 (1) Complications that endanger the life of the patient and require urgent resuscitation. (2) The subject or guardian requests to withdraw from the trial. (3) Other circumstances that, in the judgment of the investigator, warrant withdrawal from the trial.
Determination of sample size	
Two hundred subjects were to be enrolled in this study and divided into a successful extubation group and a failed extubation group according to the final extubation outcome. As there is no previous literature assessing the value of combined cardiopulmonary and diaphragmatic indicators to predict extubation, it was not possible to calculate a formal sample size, referring to previous literature examining the effect of single factors and the pre-trial main efficacy indicator of successful extubation, which was 70% for the conventional group and 100% for the pulmonary ultrasound group. The software PASS (version 21.0.3) was used to calculate that 166 patients were required for this trial at the 0.05 (one-sided) significance level. (taking into account a 10% shedding rate), which provides a 90% certainty test to obtain validity results for the test group compared to the conventional group.

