Statistical analysis	
The general principles of descriptive statistical analysis in this study were as follows.
 
SPSS 22.0 was used for statistical analysis. Continuous measures were expressed as ($\bar{x} \pm s$) and tested for normality, and independent samples t-test was used for comparison of normally distributed data between the two groups. The χ^2 test was performed for statistical data to verify whether there was a statistical difference between the groups. $p < 0.05$ was statistically different.
 
Logistic regression model analysis was applied to derive prediction models for lung ultrasound score, diaphragm mobility and oxygenation index. ROC curves were plotted for lung ultrasound score, transthoracic cardiac ultrasound, diaphragm mobility, oxygenation index and the combined predictors, the area under the curve (AUC) was calculated for the subjects, the best cut-off value was selected, sensitivity and specificity were calculated and the predictive value of the above indicators was evaluated.

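### The study design calls for a five-index combined ROC curve, but the only regression stated names three indices and omits both cardiac ones

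*Protocol*

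**What the plan says.** All places are rows of the protocol's Programme Summary.

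- **Study design** defines the combination: "The ROC curves of the combined predictors of LUS, MAPSE, TAPSE, DD and OI were plotted". It then asks for the AUC, an optimal threshold, sensitivity and specificity.
- **Statistical analysis** states one regression: "Logistic regression model analysis was applied to derive prediction models for lung ultrasound score, diaphragm mobility and oxygenation index". The next sentence plans ROC curves for lung ultrasound score, transthoracic cardiac ultrasound, diaphragm mobility, oxygenation index and the combined predictors, again with a best cut-off, sensitivity and specificity. It does not list the members of the combination.
- **Determination of sample size** describes the novelty of the trial as a combination that includes the heart: there is "no previous literature assessing the value of combined cardiopulmonary and diaphragmatic indicators to predict extubation".
- **Purpose of the study**, objective 1, names the same five indices: "to evaluate the predictive value of LUS, MAPSE, TAPSE, DD and OI indicators for accurate postoperative extubation". It does not mention a combined score or a ROC curve.

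**The concern.** A ROC curve for several indices together can be drawn only once they have been reduced to one number per patient. Here the fitted logistic model would supply that number. The model in the protocol has no cardiac term, and no other model, weighting or rule brings MAPSE and TAPSE into a score. Followed literally, the Statistical analysis row gives a combined curve without the heart, which is not the curve in the Study design row.

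The protocol is not silent on the model. It names one, and that model disagrees with its own design. An analysis plan written from one row would inherit three indices and one written from the other would inherit five. While both stand, the choice could be made after the curves have been seen.

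**Working it through.** **1. The index lists side by side**

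| Index | Combined curve (Study design) | Regression (Statistical analysis) | Single-index curve (Statistical analysis) |
|---|---|---|---|
| LUS | yes | yes | yes |
| DD | yes | yes | yes |
| OI | yes | yes | yes |
| MAPSE | yes | no | as cardiac ultrasound |
| TAPSE | yes | no | as cardiac ultrasound |

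Five minus three leaves two indices, both cardiac, with no place in any stated model. The protocol gives no figure for the combined curve, so there is none to reproduce.

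**2. Does another reading close the gap?**

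- If the plural *models* means three single-index models, no stated model yields any combined score.
- If the combined predictors under Statistical analysis are the three regressed indices, that row contradicts Study design.
- If they are the five indices, the model that combines them is not stated.

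**3. What three rather than five indices could do to accuracy (illustration)**

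Assumptions, none of them from the protocol: normal indices, each differing by d = 0.5 SD between failures and successes, with equal pairwise correlation ρ; 180 evaluable patients (200 less 10%; the protocol attaches its 10% to the calculated 166); and 5% to 30% failures, that is 9 to 54. The 70% and 100% success rates under Determination of sample size are group figures, not a cohort rate.

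With ideal weights and k indices, AUC = Φ(√(D²/2)), where D² = k·d² / (1 + (k − 1)ρ).

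- ρ = 0: D² is 0.75 for three and 1.25 for five; AUC 0.730 and 0.785, gain about 0.055.
- ρ = 0.3: D² is 0.75/1.6 = 0.469 and 1.25/2.2 = 0.568; AUC 0.686 and 0.703, gain 0.017.
- ρ = 0.5: D² is 0.75/2 = 0.375 and 1.25/3 = 0.417; AUC 0.668 and 0.676, gain about 0.009.

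The independent-index gain depends on d: about 0.027 at 0.2 SD and 0.061 at 0.8 SD. It is zero if the cardiac indices are independent of the others and carry no signal.

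Estimating the weights lowers these gains. The table shows fitted logistic models with 2000 simulated trials per cell; each cell gives ρ = 0 / 0.3 / 0.5.

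| Failures | Failures per index (five) | Change in true AUC, five vs three | Five-index apparent AUC | Five-index true AUC |
|---|---|---|---|---|
| 54 | 10.8 | +0.051 / +0.010 / 0.000 | 0.799 / 0.722 / 0.697 | 0.773 / 0.684 / 0.655 |
| 18 | 3.6 | +0.048 / +0.004 / -0.005 | 0.812 / 0.743 / 0.723 | 0.761 / 0.666 / 0.635 |
| 9 | 1.8 | +0.045 / 0.000 / -0.008 | 0.831 / 0.772 / 0.755 | 0.740 / 0.644 / 0.612 |

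**4. Optimism, a separate matter that bears on the fix**

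The same simulations give the excess of apparent over true sensitivity plus specificity at the chosen (Youden) cut-off. It is 0.11 to 0.13 with 54 failures, 0.19 to 0.24 with 18 and 0.30 to 0.36 with 9.

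A bootstrap that repeats the fit and the cut-off choice was checked at ρ = 0.3 (200 data sets, 100 resamples each). Share of the Youden-index optimism removed = (apparent − corrected) / (apparent − true):

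- 54 failures: (0.374 − 0.275) / (0.374 − 0.253) = 0.099/0.121, about 80%.
- 18 failures: (0.452 − 0.287) / (0.452 − 0.222) = 0.165/0.230, about 70%.
- 9 failures: (0.530 − 0.299) / (0.530 − 0.179) = 0.231/0.351, about 65%.

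**The case against.** **The intent can largely be recovered.** The sentence after the regression lists cardiac ultrasound and ends with the combined predictors; read with Study design, that means five indices. The likeliest cause is an incomplete list in one sentence. This stands, and it is why the fix is small. It does not supply the missing model.

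**Objective 1 might seem to go unanswered.** A reader could infer this, but objective 1 asks only for the predictive value of five indicators and mentions neither a combination nor a ROC curve. The planned single-index curves still serve it. Objective 2 does name a combination, "Explicit cardiac and pulmonary ultrasound combined with diaphragmatic mobility and oxygenation index is a good guide", but for postoperative complications, so it is weak support for a model of extubation.

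**The omission might seem to cost accuracy.** The documents do not show this. With correlated indices the change is near zero or slightly negative, and the gain of about 0.05 needs all five to be independent.

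**Optimism is not caused by the three-versus-five mismatch, and validation is often left to an SAP.** The first part is right: optimism would remain if the regression named all five indices. On the second, the protocol does state its procedure, which is to fit, choose the best cut-off and report accuracy on the same patients. A better method can fairly be proposed.

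**The timing of OI might look like a contradiction.** Study design says "arterial blood was drawn to determine OI using a blood gas analyser" in patients about to be extubated, and PaO2/FiO2 is listed with the end-of-SBT values. The P/F formula follows a later sample: "After extraction, another arterial blood gas is drawn and the arterial partial pressure of oxygen is analysed". That formula can be read as a definition only, so the time point merely needs stating.

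**Conclusion.** The point holds for the combined curve alone. The protocol asks for a five-index combined ROC curve and states no model that produces it; its one regression has three indices and no cardiac term. This rests on the text and needs no assumption. It should be corrected, but it does not invalidate the single-index analyses.

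The numerical consequence is unknown because the protocol gives neither effect sizes nor an overall failure rate. Under the equal-effect assumptions above, the change in true AUC runs from slightly negative to about 0.05. The defect is a stated model that does not match the stated design, not a demonstrated loss of accuracy.

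**What to change.** Under Statistical analysis, state one logistic regression of 48-hour extubation failure on LUS, MAPSE, TAPSE, DD and OI, and name it as the source of the combined ROC curve. If a three-index model is also wanted, label it secondary and do not call it the combined predictors. As a clarification, say that OI in the model is the end-of-SBT value.

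Report AUC, sensitivity and specificity of the combined score with a bootstrap optimism correction that repeats both the fit and the cut-off choice in each resample, and give the number of failures beside them. If failures are few, present the five-index score as exploratory next to the single-index curves.

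The cost is one sentence for the model, a phrase for the OI time point and a short script. All five indices are already collected. There are three downsides:

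- Reported accuracy will be lower.
- With few failures the five-index model is unstable. At 9 to 18 failures and correlation 0.5, its true AUC is 0.005 to 0.008 below that of the three-index model.
- The bootstrap removes only part of the optimism, and less of it as failures become fewer.

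### As written, the combined model and every cut-off are chosen and scored in the same 200 patients, which on average overstates the combined AUC and the sensitivity and specificity at those cut-offs

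*Protocol*

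**What the plan says.** The first main objective in the Programme Summary is "to evaluate the predictive value of LUS, MAPSE, TAPSE, DD and OI indicators for accurate postoperative extubation". The Study design entry plans to "conduct a multicentre prospective clinical trial of 200 elderly patients", and the cohort is divided only by extubation outcome.

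The analysis is described twice:

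- **Study design:** "The ROC curves of the combined predictors of LUS, MAPSE, TAPSE, DD and OI were plotted", after which "the optimal threshold value was selected, the sensitivity and specificity were calculated, and the predictive value of the above indicators was evaluated".
- **Statistical analysis:** "Logistic regression model analysis was applied to derive prediction models for lung ultrasound score, diaphragm mobility and oxygenation index". ROC curves and their AUCs follow for the individual indicators and for the combination, and then "the best cut-off value was selected, sensitivity and specificity were calculated and the predictive value of the above indicators was evaluated".

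The first description combines five indicators, while the logistic model in the second names three. Neither mentions a hold-out sample, cross-validation, a bootstrap, or a cut-off fixed in advance.

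**The concern.** Two steps use the outcomes of the same patients twice.

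1. The logistic weights are chosen to separate failures from successes in these 200 patients, and the AUC of the resulting score is then computed in them. Part of the separation is noise that will not recur.
2. A cut-off is picked because it performs best in these patients, and its sensitivity and specificity are then read off in them. This applies to a single marker as well as to the combined score.

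Predictive value is the trial's first main objective, so these are its headline numbers. The effect is also uneven. The AUC of a single marker involves no fitting and carries no such bias, whereas the combined AUC does. Setting the two side by side uncorrected therefore tilts the picture towards the combination.

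**Working it through.** **Plan's own figure.** The protocol gives no target or expected value for AUC, sensitivity or specificity, so there is nothing to reproduce on this point. The 166 in Determination of sample size belongs to a two-group comparison of success rates and does not bear on optimism.

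**Inputs from the protocol**

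- N = 200, one cohort (Study design).
- Five predictors (Study design) or three (Statistical analysis).
- Success rates of 70% and 100% (Determination of sample size). If all 200 behaved like the 70% group, failures would be 0.30 × 200 = 60. An even mix of the two rates gives (0.30 + 0)/2 = 15%, or 30 failures. Neither is stated as an expectation for this cohort.

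**Assumptions**

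- Failure rates of 30%, 15% and 10% (60, 30 and 20 failures), with 5% (10 failures) as an extreme.
- The best cut-off means the maximum of the Youden index, J = sensitivity + specificity − 1.
- Independent normal markers of equal strength, with a true combined AUC of 0.70 or 0.80.

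**Set-up.** For a normal score with unit variance and mean difference δ, AUC = Φ(δ/√2). With P equally strong markers, each has difference δ/√P. For AUC 0.80, δ = √2 × 0.8416 = 1.190. With P = 5, each marker has 1.190/√5 = 0.532 and a single-marker AUC of Φ(0.532/√2) = 0.647.

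**Calculation.** 1,500 simulated data sets per setting. Optimism = (mean in the same patients) − (mean for the same model and cut-off in new patients). Differences are taken from the rounded values shown.

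| Failures | Predictors | True AUC | AUC, same / new (diff) | Sensitivity, same / new (diff) | Specificity, same / new (diff) |
|---|---|---|---|---|---|
| 60 | 3 | 0.80 | 0.805 / 0.795 (0.010) | 0.757 / 0.699 (0.058) | 0.744 / 0.726 (0.018) |
| 60 | 3 | 0.70 | 0.710 / 0.691 (0.019) | 0.687 / 0.616 (0.071) | 0.672 / 0.646 (0.026) |
| 60 | 5 | 0.80 | 0.810 / 0.790 (0.020) | 0.761 / 0.695 (0.066) | 0.749 / 0.723 (0.026) |
| 60 | 5 | 0.70 | 0.718 / 0.683 (0.035) | 0.689 / 0.605 (0.084) | 0.680 / 0.647 (0.033) |
| 30 | 3 | 0.80 | 0.808 / 0.792 (0.016) | 0.777 / 0.684 (0.093) | 0.744 / 0.731 (0.013) |
| 30 | 5 | 0.80 | 0.818 / 0.784 (0.034) | 0.786 / 0.669 (0.117) | 0.753 / 0.735 (0.018) |
| 20 | 3 | 0.80 | 0.812 / 0.789 (0.023) | 0.791 / 0.664 (0.127) | 0.753 / 0.742 (0.011) |
| 20 | 3 | 0.70 | 0.720 / 0.681 (0.039) | 0.721 / 0.566 (0.155) | 0.686 / 0.671 (0.015) |
| 20 | 5 | 0.80 | 0.820 / 0.778 (0.042) | 0.795 / 0.640 (0.155) | 0.760 / 0.748 (0.012) |
| 20 | 5 | 0.70 | 0.737 / 0.665 (0.072) | 0.735 / 0.542 (0.193) | 0.695 / 0.676 (0.019) |

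A separate run with five markers and an attainable AUC of 0.75 falls inside this grid:

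- 10% failures: AUC 0.779 − 0.723 = 0.056; sensitivity 0.765 − 0.590 = 0.175.
- 30% failures: AUC 0.764 − 0.737 = 0.027; sensitivity 0.724 − 0.648 = 0.076.

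**Single marker, true AUC 0.70.** The empirical AUC shows no bias (0.701 against 0.700). Sensitivity at its chosen cut-off does: 0.718 − 0.613 = 0.105 at 10% failures and 0.682 − 0.630 = 0.052 at 30%.

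**Extremes.** With 10 failures and five predictors, optimism is 0.07 to 0.12 in AUC and 0.27 to 0.33 in J. Five markers with no predictive value at all (true AUC 0.50) still give an apparent AUC of 0.64 at 10% failures and 0.59 at 30%.

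**The case against.** **The protocol is silent, and the SAP is not shown.** Internal validation is often left to the SAP, and the entry describes its contents as general principles. This stands in part: one can say only that this protocol describes no correction. A reader might infer that the trial has ruled one out or will certainly report uncorrected figures, and the document does not support that. The protocol does, however, state a full sequence from model fit to evaluated predictive value. That sequence yields apparent performance unless something is added to it.

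**Not everything is inflated.** A reader might take every AUC to be too high. The single-marker AUCs, which are a main output, are not, and this objection stands in full.

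**At many failures the AUC bias is small.** With 60 failures, 140 successes and AUC 0.75, the Hanley-McNeil standard error is about 0.04, so a bias of 0.02 is about half a standard error. For single-marker sensitivity, the bias of 0.052 compares with √(0.63 × 0.37/60) = 0.062. This is fair for those two quantities. For the five-marker sensitivity the bias is 0.076 against √(0.648 × 0.352/60) = 0.062, which exceeds one standard error. An interval centred on the apparent value also ignores the bias altogether. The only rate in the protocol that implies failures is the 70% success rate, and nothing says that it applies to this cohort, so lower failure rates cannot be excluded.

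**No formal comparison of combined with single markers is planned.** This is correct. A paired test should not be demanded, and the point about an uneven comparison matters only if such a comparison is made.

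**Conclusion.** The concern holds in a limited form. Carried out as the protocol states, the analysis overstates on average the combined-model AUC, and the sensitivity and specificity at every data-chosen cut-off.

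For N = 200, a Youden cut-off, three to five predictors and 30% down to 10% failures, the usual size is as follows:

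- **Combined AUC:** about 0.02 to 0.06 too high. The corners of the grid reach 0.01 (three strong predictors, 60 failures) and 0.07 (five weak predictors, 20 failures).
- **Combined sensitivity:** about 0.07 to 0.18 too high, with corners at 0.06 and 0.19. Specificity is affected much less, by 0.01 to 0.03.
- **Single-marker sensitivity:** about 0.05 to 0.11 too high. Single-marker AUC is unaffected.

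The failure rate, the true AUC, the Youden rule and the independence of the markers are assumptions. The number of failures drives the size most. These are average effects, so a reader should not infer that any one reported figure must be too high, or that an advantage of the combination would be spurious. Because the predictor set is stated in two ways, the model to be validated is not yet fixed.

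**What to change.** 1. Name one predictor set for the combined model, and make Study design and Statistical analysis agree on it.
2. Add a sentence on internal validation: draw bootstrap resamples (for example 1,000), repeat both the model fit and the cut-off selection in each, and score each result in its resample and in the original 200. Corrected value = apparent value − mean of (performance in the resample − performance in the original data). For single markers, only the cut-off selection needs repeating.
3. Report the corrected combined AUC, and corrected sensitivity and specificity for all selected cut-offs. Label uncorrected values as apparent. Single-marker AUCs can be reported as they are.
4. If the combination is set against single markers, use its corrected AUC.

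If the SAP already contains this, a cross-reference is enough once the predictor set is settled. The cost is a few sentences, a little more code and somewhat less favourable headline figures, with no extra patients or measurements.
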